We propose a 6-month pilot single blind, randomized clinical trial (RCT) comparing social dancing (ballroom dancing) versus active control (walking) in 32 older adults at high risk of dementia. Our **overall hypothesis** is that social dancing in cognitively vulnerable seniors will induce neuroplasticity that will enhance cognitive processes and improving everyday behaviors. Our **objective** for this pilot trial is to examine feasibility as well as obtain preliminary data on intervention effects (trajectory and asymptote) on EF to design a full-scale RO1.

Aim 1: Obtain preliminary data regarding feasibility and effects on cognition of social dancing in seniors at risk for dementia. Dementia at-risk status is defined as cognition lower than expected for age (see 2.B for justification and criteria); similar approach was used in recent lifestyle interventions trials with cognitive outcomes.¹⁴⁻¹⁷ While preliminary studies support a possible cognitive benefit of dancing, most studies have not targeted older individuals at high risk for dementia, a highly prevalent group with faster rates of cognitive decline. We will, hence, establish **feasibility** of conducting social dancing intervention in seniors at risk for dementia (see **Table 1** for feasibility parameters).

We will track changes in a **composite EF score** derived from a battery of standardized (Digit symbol substitution test: DSST),¹⁸ computerized (Flanker test),^{19, 20} and cognitive-motor (Walking While Talking: WWT) tests to capture various facets of this broad domain. Composite cognitive scores were used to define outcomes in many recent RCTs.²¹⁻²³ We will administer tests at baseline, month 2, month 4, month 6 (end of intervention) and month 9 (3 months post-intervention) to determine **trajectory (as well as any asymptote) on improvement** in both groups that will help plan optimal duration for our full-scale RO1. These highly reliable EF tests were used to show exercise effects on cognition,^{8, 24-27} and predict cognitive (dementia) and non-cognitive outcomes (falls).²⁸⁻³¹ The composite EF score helps overcome limitations of single EF tests.²¹⁻²³

Aim 2: Explore functional and structural neuroplasticity for cognitive benefits of social dancing in seniors at risk for dementia. We will explore neuroplasticity in functional activation/deactivation and structural connectivity patterns as a function of social dancing (pre-post intervention). We will use **functional Magnetic Resonance Imaging (fMRI)** to investigate neuroplasticity in functional activation/deactivation patterns with our validated 'imagined WWT' task³²- as well as with DSST and Flanker tests, which are responsive to physical interventions.²⁵ *We predict that compared to walking, dancing will result in greater intervention-related changes in functional activation of supplementary motor, anterior cingulate and prefrontal regions during imagined WWT, DSST and Flanker tests.*

To investigate neuroplasticity in structural connectivity patterns, we will use **diffusion-weighted imaging**, which are responsive to social dancing and physical interventions.^{33, 34} We predict that compared to walking, dancing will result in greater intervention-related changes in structural connectivity patterns, including fornix and cingulum.

Social dancing appeals to older adults, has intrinsic value, is enjoyable, and has high potential for sustainability. This R21 proposal is novel and high risk, but will provide the evidence base to develop a

definitive full-scale RCT to support or refute prescription of social dancing to prevent cognitive decline in older adults at high risk of AD and related dementias.

2) Study Design

Overview and Design. We propose a pilot single blind RCT of social dancing versus walking in 32 dementia at-risk seniors (16/group). For Aim 1, outcome is change in EF composite score measured with a comprehensive battery of conventional (DSST), computerized (Flanker test) and cognitive-motor (WWT) EF tests assessed at baseline, month 2, month 4, month 6 (immediate post-intervention), and 3 months post-intervention to derive trajectories to inform design of future R01. Feasibility is assessed through metrics described in Table 1. For Aim 2, outcome is neuroplasticity measured using our *validated fMRI iWWT protocol, DSST and Flanker Tests, and white matter integrity*.

- a) **RECRUITMENT AND SCREENING:** We will enroll 32 dementia at-risk seniors over 2 years. **Our sample size is not based on demonstrating clinical efficacy but to obtain preliminary data and feasibility to plan our R01.** We will contact a random sample of individuals age 65 and over identified from local population lists as well as from the large clinical population in our health system. Both sources were used to recruit ~3000 participants for our aging studies.³⁵⁻³⁷ A letter explaining our study is followed by a telephone call. Those expressing interest on the telephone are screened with Memory Impairment screen (**MIS**)³⁸ and **AD-8**³⁹ to establish dementia-risk status. Potential recruits will be invited for an in-person visit where final eligibility is determined. Written consent and screening is at our research center. **An independent DSMB will be constituted prior to the start of the study.**
- b) **ELIGIBILITY CRITERIA.** Our target population is dementia at-risk seniors. Patients will be evaluated by research assistants followed by the study clinician to assess eligibility for the trial.
 - i) Inclusion criteria: **1)** Age 65 and older. **2)** 'At-risk for dementia' status defined as meeting cutscores on either MIS (≤ 6) or AD-8 (≥ 1) tests. The MIS is a 4-item dementia screener developed in our Bronx population.^{38, 40} MIS accounts for various educational levels.⁴¹⁻⁴⁴ The AD-8 is a 2-minute screener with high validity for detecting dementia.^{39, 45} AD-8 is less educationally biased as it does not test patients on acquired learning. AD-8 is culturally neutral as it focuses on changes in basic activities in which everyone engages. Both tests correlate highly with dementia pathology.^{46, 47} We used these 2 screeners to enroll 3000 participants in 3 NIH funded studies.^{38, 48, 49} We decided against MCI as a criterion, as its prevalence is low (<12% in our community-based cohort⁵⁰); limiting generalizability. We examined validity of our '**dementia at-risk**' definition in 543 older adults in the Einstein Aging study;⁴⁸ 176 met dementia at-risk criteria (prevalence 32%). Over a mean follow-up of 1.5 years, 'dementia at-risk' status predicted incident cognitive impairment (any of MCI, Motoric cognitive risk syndrome (MCR)^{51, 52} or dementia) (HR adjusted for age, sex, education and illnesses 2.0, 95%CI 1.1-3.8). Hence, our definition captures a high-risk yet highly prevalent group. **3)** Sedentary: exercises less than the CDC recommended level of 150 min moderate intensity activity/week.⁵³ **4)** Agree to neuroimaging: more efficient to enroll those who also meet imaging criteria for this pilot. We recruited >100 participants in the last 2 years for various imaging studies.
 - ii) Exclusion criteria: **1)** Active medical or major psychiatric illnesses. **2)** Musculoskeletal/cardiovascular mobility limitations. **3)** Competitive dance or regular social dance (>1/month). As seniors may occasionally dance at social events (but not at dose for cognitive benefits), excluding all seniors who ever danced is not practical. **4)** Presence of dementia¹⁰⁶ (telephone or in-house evaluation). **5)** Standard imaging exclusions. It will not be feasible to obtain MRI or other biomarkers to screen and enroll participants. However, the pre-intervention MRI for Aim 2 will allow us to stratify the at-risk group into those with or without brain pathology (e.g. hippocampal atrophy⁵⁴) for exploratory analyses.
- c) **RANDOMIZATION.** Eligible participants are randomized for interventions at initial visit, stratified by gender and age (< or >80 years). Equal number of men and women will be enrolled. Group assignment is generated by [name], who is not involved in subject testing or interventions. She will generate an encrypted file with the randomization order to assign participants to the study arms. She will be the only one with access to the list. To avoid attrition following enrollment, we will not wait to recruit all participants to start the interventions but will have rolling admission into the dance and walking classes.

- i) **Social Dance (intervention arm):** 90-min dance sessions twice weekly for 6-months. The session includes warm-up, dance and cool down. The program includes Foxtrot, Waltz, and Latin dances. The choice of multiple dances is pragmatic since it mirrors the choice offered in senior centers and avoids tedium of only doing one dance form. Intensity will not be manipulated to mimic exercise training as in aerobic dance classes. Dance instructors are experienced in teaching seniors (see LOS from USA Dance). Progression to new dances will be gradual and take into account balance, cardiac and cognitive demands. Methodological structure is the same for all sessions. The instructor will demonstrate the dance sequence. Participants warm up with gentle stretches. The instructor will repeat dance sequence several times and the participants will try to reproduce it along with the instructor, until sequence is learned. When participants execute the dance sequence satisfactorily, they will reproduce it along with the music.
- Duration (6 months), frequency (2/wk) and intensity** based on earlier dance studies and pragmatic considerations. A review of dance interventions for various health outcomes (including cognition) concluded that dance programs should provide a minimum of one 45-minute session per week for 6 weeks (lower than our study).⁵⁵ The dose of exercise in both dancing and walking arms is higher than the CDC recommended exercise dose.⁵³
 - Pairing** at dances is at random and the instructor will ensure participants rotate partners.
 - Performance monitoring:** Intensity measurement via **accelerometers** and cardiac monitoring during dance lessons.
 - Dancing integrates **physical, cognitive and social elements**. Our interventions may also improve **mood, self-esteem, and self-efficacy**.^{56, 57} We will measure each of these components. However, a detailed mechanistic examination of which dance components contribute to cognitive benefits is beyond the scope of this pilot study, and will be done in our future RO1. Randomization is also a powerful tool to address biases due to confounders.
- ii) **Walking (active control):** We completed a pilot walking study in frail seniors supporting feasibility.⁵⁸ Participants meet twice weekly for 6-months matching frequency and intensity in the dance group. Recent reviews report minimal to no cognitive benefits from exercise programs in cognitively impaired seniors.^{26, 59-61} Walking exercises was reported in another review to show modest EF benefits in healthy but not cognitively impaired seniors (our focus).⁶² [name] was part of the LIFE study that reported that moderate-intensity physical activity program (walking) in sedentary seniors did not improve global or domain-specific cognitive function (including EF) compared to those in a health education program.⁶³ A recent review by the National Academy of Medicine concluded that the evidence was encouraging but inconclusive regarding cognitive benefits of exercise, and further research was required.⁶⁴
- Procedure:** The protocol is based on American College of Sports Medicine⁶⁵ and American Heart Association⁶⁶ recommendations for seniors. Additional details are in our published report.⁵⁸ Briefly, each session starts with 5-10 minutes of warm-up walking at comfortable speed. Speed is gradually increased to the level at which participants felt it is 'somewhat hard' (12-14 Borg scale^{67, 68}) for two 35 minute sessions with breaks in between followed by 5-10 minute cool down period (total 90 min to match dance group). Training interval is gradually increased over the first 2 weeks.
 - Environment:** The indoor environment that is less subject to weather and other barriers when walking outdoors.
 - Social interactions:** To match the social aspect of dance, treadmills will be arranged in clusters. The proportion of men to women is the same as in the dance group. Music will be played during treadmill sessions to minimize variability.
- d) **OUTCOMES Aim 1 (Cognition):** As EF includes multiple cognitive processes; a single test is not sufficient. We will examine a **composite EF score** by summing standardized scores on the 3 tests. Composite cognitive scores were used in many RCTs.²¹⁻²³ We will also compare trajectories in individual tests to gain insights into study design of our full-scale RO1. Study outcomes will be assessed at baseline, month 2, month 4, post-intervention (end of month 6), and 3 months post-intervention (month 9).

- i) **Digit Symbol Substitution test (DSST)** is a timed test that assesses speed of processing, visuo-spatial attention and EF. DSST predicts cognitive (dementia) and non-cognitive outcomes (falls). DSST is amenable to exercise.⁶⁹
- ii) **Flanker Test** is in the NIH toolbox.^{19, 20} It measures attention and inhibitory control. The Flanker test was used to demonstrate exercise effects on EF.^{8, 70}
- iii) **Walking While Talking test (WWT)** is an EF-dependent everyday behavior measure developed by our group.^{29, 30} Dual-tasking assessed by WWT is a defined facet of EF,^{36, 71} and associated with increased prefrontal activation.⁷² Participants walk on an instrumented walkway for 2 trials reciting alternate letters of the alphabet.⁷³ See our published papers for WWT procedures.^{28-30, 72-74} WWT has excellent test-retest and inter-rater reliability.²⁸⁻³⁰

Blinding: While double-blinding both subjects and testers is not feasible, the following steps (besides randomization) are included: A. Selection bias reduced by concealing treatment allocation until subject enrolled.⁷⁵ B. Outcome is an objective endpoint and not subjective reports.⁷⁵ C. Dance and walking groups meet non-overlapping times. D. Each aspect of the RCT is supervised independently: interventions ([name]), assessments ([name]) and imaging ([name]). E. Participants/staff instructed not to disclose group assignment or interventions.

Learning effects: We will utilize 4 complementary approaches to attenuate practice effects⁷⁶: (1) Practice pre-baseline to reduce task familiarity effects; (2) Item-specific driven improvements minimized by using tasks with multiple similar items and standardized encoding; (3) We developed alternate forms for the WWT task,⁷⁴ and alternate forms of the DSST are available; and (4) use of control group.

- e) **OUTCOME Aim 1 (Feasibility):** Metrics below will identify barriers and refine design of our full scale RCT.⁷⁷

Metric	Measurement	Comments
Recruitment	Analyze recruitment sources by PI.	Monitor to improve recruitment rates and identify barriers.
Implementation	Proportion completed successfully. Observe all phases to find bottlenecks	Compare completion rates by education. Testers feedback on non-completion and other barriers to develop solutions.
Retention	Retention rates to be reported. 20-25% attrition common in high-risk samples.	Dancing program implemented in frailty and dementia. ^{6, 15, 78-82} Make-up sessions provided. Transportation and snacks will be provided. Dose/frequency accounted in analyses. Compensation at \$10/session consistent with IRB guidelines, and has been reported to promote adherence in exercise programs. ⁸³
Safety	Staff monitoring/DSMB oversight	DSMB and safety procedures
Practicality	PI, staff and subject observations	Extent to which intervention can be done with available resources
Acceptability	Post-study interviews of participants	Help refine RO design and enhance generalizability
Reporting	Report pilot study design and results	CONSORT guidelines will be followed: See ref ⁸⁴ for details.

- f) **OUTCOME Aim 2 (Neuroplasticity):** Encouragingly, pilot dance intervention trials have shown neuroplasticity with similar or smaller samples (12 to 48) over 6-months or less,^{3, 85-89} including the FAST study³⁴. Our primary neuroimaging measure is task-based fMRI because functional brain changes are a more sensitive biomarker of AD than gray matter volume. Our exploratory neuroimaging measure is DTI because it has been shown to be sensitive to aerobic exercise³³ and social dancing intervention.^{34, 90} Furthermore, functional and structural changes may occur before the emergence of cognitive symptoms in dementia.⁹¹⁻⁹⁵

- i) **Task-Based fMRI (Primary):** We will examine functional activation/deactivation changes pre-post intervention in both groups during an imagined WWT (iWWT) protocol developed by our group.³²

The iWWT is strongly correlated with actual WWT performance, and engages a distributed network of brain regions, including cerebellar, precuneus, supplementary motor and other prefrontal regions.³² The iWWT protocol involves 5 repeated blocks of imagined walking (iW), imagined talking (iT), and iWWT, and takes 12 minutes to administer. We will also examine functional activation/deactivation changes during DSST and Flanker tests. We will use a DSST task adapted for use in an fMRI environment and validated in older adults.⁹⁶ This task takes about 10 minutes and has 2 practice and 5 testing blocks, with 18 items each (total 95 test items). We will also use a Flanker task optimized for fMRI environment, with a 4-minute practice block and three 4-minute test blocks for a total of 120 test items (60 congruent, 60 incongruent) presented with jittered inter-stimulus intervals (4-8 sec).⁹⁷ *We predict that dance will increase activation in supplementary motor, anterior cingulate and other prefrontal cortex regions during the iWWT, DSST and Flanker tasks to a greater extent than walking.* We expect treadmill training to increase activation in the somatosensory cortex and the cerebellum. Jovancevic et al noted differences in activation in response to DSST on fMRI in 5 women (mean age 55) in the left middle frontal gyrus, right inferior parietal lobule, and left angular gyrus following a 6-week video dance program.⁹⁸

- ii) **Diffusion-Weighted Imaging (exploratory).** We propose to examine **pre-post changes in structural connectivity** as a function of social dancing. Structural changes in white matter integrity have been observed following physical and social dancing interventions.³⁴ Based on these initial findings, we propose to monitor structural changes in white matter integrity (fractional anisotropy) using Tracts Constrained by Underlying Anatomy (TRACULA).⁹⁹ *We expect that dance will change white matter integrity in fornix, cingulum and over frontal integrity to a greater extent than walking.*
- g) **Other measures:** We will collect other measures to explore the broader impact of dancing. Given R21 space limits, these measures are summarized in Table 1. We have administered 3-hour test batteries to over 3000 participants in our other aging studies with minimal attrition.

Table 1. Summary of secondary outcomes, covariates and process measures

Domains	Tests and procedures (refs)	Description (0,2,4,6, 9 months)	Time
Clinical	Study clinician evaluation ^{35, 100} of neurological and musculoskeletal systems including gait	Standardized examination and CDR rating. Clinicians Global Impression of Change ^{101, 102}	30 m
Cognitive	Neuropsychological battery ¹⁰³	Test of multiple cognitive domains. ¹⁰³	60 m
	CHAMPS ¹⁰⁴	Lifestyle changes baseline and post-intervention	15 m
	Gait variables	GAITRite	10 m
	Balance	Unipedal stance, trunk sway (covariate)	5 m
	ADL scales	Monitor changes in function	5 m
Mood	Geriatric depression scale ¹⁰⁵	Depressive symptoms (covariate)	5 m

3) DATA AND SAFETY MONITORING PLAN:

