- **Intensity** (*actigraphy in-session*) and **dose** (*number of sessions*) of dance and walking will also be examined.

Power: The pilot sample size was based on pragmatics of recruitment and necessities for examining feasibility.¹¹⁹ Based on previous studies, we expect correlations of at least 0.80 between repeated EF scores. With 16 in each group and assuming 20% drop out rate at post intervention, we can detect a difference of 0.075 SD per month in EF slope using measurements at baseline/2/4/6 months, between groups with 80% power using 2-sided tests with alpha level 0.05.

- b) **Aim 2:** The comparison of imaging measures pre-post intervention (month 0 vs. 6) between study arms will be analyzed using multivariate covariance-based analyses, adjusting for age, gender and other covariates. Multivariate covariance-based analyses are particularly sensitive to detecting effects in the presence of between-subject variability and collinearity– issues particularly important to consider in aging populations and with neuroimaging data. Drs. [name] and [name] have considerable experience with these neuroimaging analyses.^{96, 120-127} Mean and confidence intervals of imaging measures within each group as well as the difference between the two groups will be reported for performance at each time point of pre and post intervention, and for change at post from pre intervention.

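### If the exploratory MRI marker is graded, the planned with/without-pathology split discards about a third to a half of its information; using the baseline value as a continuous term is modestly better

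*Combined protocol and SAP*

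**What the plan says.** The sentence at issue is in section 2) Study Design, b) Eligibility criteria, under exclusion criterion 5. It explains that MRI cannot feasibly be used to screen and enrol, and adds that the pre-intervention scan will nevertheless "allow us to stratify the at-risk group into those with or without brain pathology". The one example given is hippocampal atrophy, and the stated use is "for exploratory analyses".

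The sentence gives no definition of pathology, cut-off, expected share, outcome or model. Section 8) Data Analysis does not return to it. The only split described there, under Aim 2, halves each intervention group to assess reliability and has nothing to do with pathology.

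The trial has "32 dementia at-risk seniors (16/group" arms, and the Aim 1 power paragraph works "With 16 in each group and assuming 20% drop out rate at post intervention". The feasibility table in section 2 e) gives "20-25% attrition common in high-risk samples". Section 8 says the analyses are meant to estimate effects for a larger study.

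**The concern.** Hippocampal atrophy is a matter of degree. A two-group split treats people just either side of the cut as different, and everyone on one side as alike. Some of the information in a scan already paid for is lost. Because no cut-off is fixed in advance, it could also be chosen after results are seen.

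In a pilot of 32 whose product is a set of estimates, how tightly a quantity can be estimated from the available data matters, even for exploratory work. If the split were used to look at the dance effect by pathology, each arm would be divided again and the smaller cells would hold only a few people.

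**Working it through.** The plan states no cell size, prevalence, cut-off or power for this split, so there is no figure of its own to reproduce. The Aim 1 power figure concerns a different quantity (the slope of executive function by arm); only its dropout rate is used here.

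**Inputs**
- From the documents: 16 per arm; 20% dropout, leaving 16 × 0.80 = 12.8 per arm.
- Assumed: share with pathology *p* from 20% to 50%; marker normal, with a linear effect; the same share in each arm; SD of change equal to 1.

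**1. Information kept by a cut.** Relative efficiency = φ(z)² / [p(1 − p)], where z is the cut point and φ the normal density.
- p = 0.50: 0.3989² / 0.25 = 0.637
- p = 0.20: 0.2800² / 0.16 = 0.490

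The loss is therefore 36% to 51%. Thirty-two people carry the marker information of about 32 × 0.637 = 20.4 or 32 × 0.490 = 15.7.

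**2. Expected cells per arm** (with / without pathology), n·p and n·(1 − p):

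| Share with pathology | 16 per arm | 12.8 per arm |
|---|---|---|
| 50% | 8 / 8 | 6.4 / 6.4 |
| 40% | 6.4 / 9.6 | 5.1 / 7.7 |
| 30% | 4.8 / 11.2 | 3.8 / 9.0 |
| 20% | 3.2 / 12.8 | 2.6 / 10.2 |

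**3. Precision of a difference in dance effect between the two groups**, if that contrast is what is examined. With 12.8 per arm, SE = √{2[1/(12.8p) + 1/(12.8(1 − p))]}. The 95% half-width uses t on 22 df (25.6 − 4, rounded) = 2.074.
- p = 0.50: SE = √0.625 = 0.791; half-width 1.64 SD of change
- p = 0.20: SE = √0.977 = 0.988; half-width 2.05 SD

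**4. The same contrast from a continuous term.** The arm-by-marker slope has SE = √(2/12.8) = 0.395 per SD of marker. To compare like with like, multiply by the gap in mean marker value between the two groups, φ(z)/p + φ(z)/(1 − p).
- p = 0.50: gap 1.596; half-width 1.596 × 0.395 × 2.074 = 1.31 SD
- p = 0.20: gap 1.750; half-width 1.750 × 0.395 × 2.074 = 1.43 SD

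The ratios are 1.31/1.64 = 0.80 and 1.43/2.05 = 0.70, the square roots of the efficiencies in step 1. The CI is about 20% to 30% narrower.

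**5. How much this matters for power.** Simulation with 26 people (13 per arm), 4,000 runs per setting:

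| Interaction (SD of change per SD of marker) | Continuous | Median split | 20/80 split |
|---|---|---|---|
| 1.0 | about 60% | about 40% | about 25% |
| 0.5 | about 20% | about 14% | about 10% |
| 0.3 | about 10% | about 8% | about 6% |

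For scale, the main effect used in the Aim 1 power statement is 0.075 × 6 = 0.45 SD over six months. At the stated correlation of 0.80 the SD of change is √[2(1 − 0.80)] = 0.632, so this is 0.45/0.632 = 0.71 SD of change. An interaction of 1.0 is larger than that. At 20/80, about 4% of simulated trials could not estimate the split interaction at all, because one arm had nobody on one side of the cut.

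**The case against.** The strongest reply is that this is one permissive sentence in the eligibility criteria. It says what the scan will allow, labels the use exploratory, and names no arm-by-pathology contrast; stratifying could simply mean describing the sample. That stands, and it limits the point to a suggestion about method.

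Second, pathology may be a present/absent read. The MRI safety text has a neuroradiologist review every scan for pathology, and for a finding that is binary by nature the calculated loss does not apply. That also stands, although the one example the plan gives is graded. If an effect appears only beyond a threshold, a linear term could do worse than a cut.

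Third, the continuous analysis is not precise either: half-widths of 1.31 to 1.43 SD remain wide, and at interactions of 0.3 to 0.5 the power advantage is small. True, but the gain costs almost nothing.

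Three stronger readings are tempting and are not supported:
- A reader might infer that the split is meant to choose the target group for the later full-scale trial. The documents state no such aim.
- A reader might infer that every cell falls to about 3 to 6. That range describes only the smaller cell per arm after dropout, at an assumed prevalence. With all 32, an even split gives 8 per cell, and a 20/80 split about 3 and 13.
- A reader might fault randomization for stratifying only by gender and age. The plan says MRI is not available for screening and enrolment, and chance imbalance affects a continuous moderator as well.

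**Conclusion.** The point holds as a minor improvement. The plan describes a two-group split whose only named example is graded, and nothing in section 8 replaces it. If such a marker is cut, 36% to 51% of its information is lost for pathology shares between 50% and 20%, assuming normality and linearity. The prevalence range is an assumption, because the documents give none.

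Using the continuous value narrows the CI by about 20% to 30% over the same marker gap. It does not make the estimate precise at this sample size. No primary outcome, power statement or decision rests on the split. Large power differences should not be claimed, since they appear only for an interaction bigger than the main effect the plan works with.

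**What to change.** In the eligibility section, and as a line in section 8:
- For graded markers, use the continuous month 0 value in the exploratory analyses, for example hippocampal volume relative to head size, and name the marker in advance.
- Where the dance effect is examined by pathology, enter the marker as an arm-by-marker term in the planned mixed model and report the slope with its 95% CI.
- Keep yes/no only for findings that are truly present or absent. Define them in advance and report them descriptively, with cell counts by arm.

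The cost is a change of wording and one model term. No extra visits, participants or scans are needed, provided a volume can be derived from the anatomical scan that an atrophy call would need anyway. The downside is a linearity assumption, which can be checked with a plot.
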